- c. The primary intervention effect will be examined in patients seen in the ED for chest pain/discomfort and sent home. Since the intervention messages focus on chest pain, these patients are also targets of the intervention.
- d. The primary intervention effect will also be examined in subgroups defined by factors associated with delay that might affect the effectiveness of the intervention. These are sex, race/ethnicity, age, history of previous CHD, health insurance coverage, and current event (AMI vs. unstable angina vs. other cardiac diagnoses).
- 2. Secondary Definitions of Delay Time

Since the different components of the delay interval may be affected differentially by the intervention, alternative definitions of delay time will be examined. We hypothesize that all delay times will be reduced by the intervention. The following definitions will be offered:

- a. Time from onset of acute symptoms to taking action to seek care (e.g., time of calling 911) because this reflects patient recognition and action.
- b. Time from onset of acute symptoms to in-person contact with the medical care system (either the ED or the EMS) because this reflects time to contact with any available treatment.
- c. Time from onset of symptoms to receipt of reperfusion therapy (thrombolytic therapy or immediate PTCA) among those who receive such therapy.
- 3. Secondary Outcomes

We will examine the effect of the intervention on the following outcomes:

a. Receipt of early revascularization in patients with IHD diagnosis (ICD 410/411): thrombolytic therapy or immediate PTCA.

Receipt of myocardial revascularization procedures, reperfusia or artery opening therapy is hypothesized to increase because earlier arrival will increase the proportion of patients who are eligible for treatment.

b. Severity of infarction (e.g., peak CPK, peak LDH) in patients with AMI diagnosis (ICD 410)

Severity of infarction is hypothesized to decrease because earlier treatment will reduce infarct size.

c. In-hospital case-fatality rates in patients with cardiac diagnoses.

Case fatality is hypothesized to decrease because earlier treatment will reduce infarct size and improve survival.

d. Duration of hospitalization in patients with cardiac diagnoses.

Duration of hospitalization will be reduced.

e. Total community CHD mortality.

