Community contacts also serve as qualitative assessments designed to evaluate the resources and capacity of each organization to implement the proposed interventions. Discussions with key informants have yielded information regarding vested interest groups, informal networks, advocacy movements, potential community-specific barriers to intervention implementation and existing community organizations that may facilitate initiation of community activites. After baseline data are collected, contact with community leaders will be intensified in the intervention communities.

B. Characteristics of Study Communities

A number of community-specific variables were collected to assess variability across and comparability within pairs of communities. These variables include factors used to compare community sample distributions with the U.S. population and variables designated as matching criteria. In Section III., Table 1 provides variable categories and values applicable to each study community at a specific field site. The bottom of the table includes selected aggregate study percentages and comparable values based on 1990 U.S. Census statistics for comparison.

A few comments regarding figures tabulated in Table 1 simplify the interpretation of the data. Some field sites plan to combine two smaller communities to represent one study site. In this case, values shown in the table represent a weighted average of the two communities or individualized data is provided for each community. Finally, the numbers of expected emergency department visits for chest pain and discharges for myocardial infarction (ICD 410) and unstable angina (ICD 411) were estimated in some cases using data from the participating hospitals and, in other cases, using previously collected data from similar nearby communities.

VII. MEASUREMENT OF OUTCOME, PROCESS, AND IMPACT

A. Clinical Outcome Measurements

1. Primary outcome: primary definition of delay time

The primary outcome of delay time will be defined as the interval from symptom onset to arrival at the emergency department (ED) for patients admitted for possible acute cardiac ischemia and receiving a cardiac-related discharge diagnosis (ICD 410-414, 427, 428, 429, 440, 786.5). (The primary population)

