For those patients transported by EMS personnel, the interval defined as the time from symptom onset until EMS personnel arrival at patient location will also be measured (note: if arrival time to patient is not available, arrival at geographic location will be used). EMS records (appended to the patient medical record or obtained from EMS agencies) will be reviewed to determine the time of EMS arrival. Because EMS unit staffing and equipment may vary, as may availability of a tiered EMS response, the times of first arrival will be collected separately for the first basic emergency medical technician (EMT), the first defibrillator equipped and trained person (e.g., EMT-D or paramedic), and the first paramedic. These additional time endpoints will be used in subgroup analyses (see below).

c. Interval from symptom onset until initiation of reperfusion therapy

In the eligible population of patients with AMI, the time reperfusion therapy (i.e., coronary angioplasty, thrombolytic agents, or coronary artery bypass surgery) is initiated will be determined by chart review. Subgroup analyses will individually address each specific type of reperfusion therapy.

3. Secondary Outcomes

a. Receipt of early revascularization or reperfusion therapy: thrombolytic therapy, immediate PTCA, or either.

Hospital records will be reviewed to determine the receipt and timing of such therapy. Based on NHAAP guidelines, therapy within one hour of ED arrival will be considered "early."

b. Size of MI and severity of infarction

The size of MI will be estimated by use of peak cardiac enzyme levels. While standardized assays will not be available at all trial hospitals, it is expected that each institution will demonstrate satisfactory consistency of test use and standards. Data will be obtained regarding the type of test, time of peak level draw, and peak value for each enzyme ordered. The upper limit of normal will be obtained from the hospital lab on a regular basis.

Severity of infarction will be assessed by hemodynamic instability and the occurrence of ventricular arrhythmias. Hemodynamic instability will be measured by vital signs at presentation, i.e. initial heart rate and initial blood pressure upon hospital presentation.

c. In-hospital case fatality

Hospital discharge status (dead or alive) will be obtained from medical records for the primary population.

d. Length of stay (LOS)

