REACT will follow the pattern employed in the analysis of the Minnesota Heart Health Program risk factor and morbidity and mortality data (97), and adapted for the joint analysis of data from the three major U.S. trials of community heart health promotion in the 1980's (71). Pre-intervention data from all 20 communities will be combined with postintervention data from the comparison communities to model a single secular trend. The intervention effect will then be estimated as a departure from that secular trend.

7. Subgroup analyses

Subgroup analyses are often desirable to provide insight into how and for whom an intervention achieved its effect. REACT plans a number of subgroup analyses, all secondary to the primary analyses. These include assessment of the treatment effect on delay among subgroups defined by sex, ethnicity/race, age, history of previous CHD, risk status, and other variables listed in Section IV. These analyses will be patterned after the primary analyses, with appropriate caution added to their interpretation.

8. Inferential parameters

All primary and secondary analyses will employ two-tailed tests with a nominal Type I error rate of 5%.

9. Intention to treat

A commonly followed principle in rigorously evaluated trials is the intention-totreat principle, which states that participants allocated to each condition must be retained in the primary analyses, even if that requires conservative procedures to estimate data for subjects lost to followup. REACT will be relatively protected in this regard, as it is not based on a cohort design and so will not be subject to the usual loss to followup problems. At the community level, the intention-to-treat principal implies that a community must be analyzed as belonging to the treatment condition to which it was randomized, regardless of how well the intervention was implemented (in the case of an intervention community) or how much the community may have been influenced by independent REACT-like messages (in the case of a control community).

B. Analytic Methods

1. Analysis of delay time in the primary population

The primary population for whom delay times in each community will be assessed consists of all patients with confirmed MI or unstable angina. This group will be referred to as *primary patients*. For the primary endpoint, delay time is defined to be the time between onset of symptoms and arrival at the hospital.

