- c. average peak CPK in primary patients in whom it is measured;
- d. number of patients dismissed to home from the ED after presenting with complaint of chest pain or discomfort ("false positives");
- e. number of patients discharged from the hospital with confirmed acute ischemic heart disease ("true positives").

For each continuous measurement *Y*, linear regression will be performed in each community. The dependent variable will be *Y*, and the independent variable will be calendar time. As with the primary analysis, the first six months of baseline values will be considered to have occurred at time 0. The 10 slope estimates for intervention communities will be compared to those of the control communities using a two-tailed paired *t*-test at α =0.05.

XII. PUBLICATIONS, PRESENTATIONS, AND ANCILLARY STUDIES POLICY

The REACT Study is an important scientific investigation impacting public education and health care. Because of the great effort that goes into such a study and the large amount of resources used, study investigators have the right and responsibility to communicate their findings to the scientific community and to the public at large.

To minimize the probability of inaccurate data in published materials, it is the policy of REACT that all data and text considered for all papers, and all abstracts for presentation at scientific meetings, be submitted to the Publications, Presentations and Ancillary Studies (PPAS) Committee for review and approval prior to presentation or publication. Also, the Coordinating Center shall review these materials to verify that they are accurate in nature and are consistent with data used in other REACT documents and papers. (Specific procedures to achieve this policy are delineated in Appendix B: REACT Publications, Presentations, and Ancillary Studies Procedures)

The objectives of the REACT PPAS policy are:

- 1. To assure and expedite orderly and timely presentations to the scientific community of all pertinent data resulting from the REACT study.
- 2. To assure scientifically accurate presentations and papers from REACT investigators.
- 3. To assure that all investigators, particularly those of junior rank, have the opportunity to participate and be recognized in the study-wide presentations and publications of REACT data.

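### Peak CPK is averaged over all primary patients although infarct severity is defined in AMI patients, so case mix can enter the infarct-size result and a true effect is diluted

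*Protocol*

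**What the plan says.** Section IV.G.3.b names the outcome and its population: "Severity of infarction (e.g., peak CPK, peak LDH) in patients with AMI diagnosis (ICD 410"). It hypothesizes that earlier treatment will make infarcts smaller. Section VII.A.3.b gives the enzyme measure the same purpose: "The size of MI will be estimated by use of peak cardiac enzyme levels". It adds: "While standardized assays will not be available at all trial hospitals", though it expects each institution to be consistent in its own testing. It also states: "The upper limit of normal will be obtained from the hospital lab on a regular basis".

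Section XI.B.5 lists, among the continuous secondary measures (item c), "average peak CPK in primary patients in whom it is measured". For each such measure, the value itself is regressed on calendar time in each community. The ten intervention slopes are then compared with the ten control slopes by a paired t-test. No covariate, diagnosis restriction or scaling is mentioned.

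The protocol describes primary patients in two ways. Section XI.B.1 says: "The primary population for whom delay times in each community will be assessed consists of all patients with confirmed MI or unstable angina". Section VII.A.1 (and likewise IV.F) takes patients admitted for possible acute cardiac ischemia and "receiving a cardiac-related discharge diagnosis (ICD 410-414, 427, 428, 429, 440, 786.5").

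**The concern.** The outcome section and the analysis section name different populations for the same measure, and neither description of primary patients reduces to ICD 410. Patients with unstable angina or another cardiac code have no infarct whose size could be estimated, yet their CPK values enter the average.

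Two consequences follow. First, the average depends on the proportion of AMI patients as well as on infarct size. Section IV.G.3 (item i) expects more admissions for evaluation of chest pain, and this group of outcomes is hypothesized to rise because of the intervention. If the added admissions are mostly non-AMI patients with a qualifying code, mean CPK falls in intervention communities with no change in any infarct. That is the direction the protocol would read as benefit. Second, a real reduction in AMI patients is spread over patients in whom it cannot occur, so it looks smaller than it is.

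**Working it through.** **Plan's own figures.** The protocol gives no mean, SD, power or detectable effect for peak CPK, so there is no CPK figure to reproduce. The slope framework does reproduce: with L = 1.5 yr and B = 0.333 yr, V_t = L³/[3(B+L)] − L⁴/[4(B+L)²] = 0.237, as stated in Appendix C.

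**AMI share s.**
- Table 8 plans a 50/50 mix of ICD 410 and 411.
- Table 4 gives 509/1202 = 42% for raw discharges.
- With Table 8's validation rates (90% for 410, 60-80% for 411), the validated share is 0.45/(0.45+0.40) = 53% to 0.45/(0.45+0.30) = 60%.
- Section X.A says that broadening eligibility roughly doubled the usable sample. If none of the added cases is AMI (an assumption), a 50% share becomes 25% and a 42% share becomes 21%. The last figure is a low-end assumption, because it halves a share of raw discharges.

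**CPK ratio m** (mean in AMI over mean in non-AMI patients). This is not in the documents; I assume 3, 5 and 10.

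**Pooled mean**, in units of the non-AMI mean: A = s·m + (1 − s).

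*Mix shift, infarcts unchanged.* If non-AMI cases rise by 20%, the share becomes s₁ = s/[s + 1.2(1 − s)]:
- s = 0.50: s₁ = 0.5/1.1 = 0.455
- s = 0.25: s₁ = 0.25/1.15 = 0.217
- s = 0.21: s₁ = 0.21/1.158 = 0.181

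For example, with s = 0.50 and m = 3, A goes from 2.00 to 1.91, a fall of 4.5%.

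*Dilution.* A true 10% fall in AMI patients reads as 10% × s·m/A. For s = 0.21 and m = 3 this is 10% × 0.63/1.42 = 4.4%.

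| AMI share | Fall in pooled mean from 20% more non-AMI cases (m = 3 / 5 / 10) | Apparent size of a true 10% fall (m = 3 / 5 / 10) |
|---|---|---|
| 50% | 4.5 / 6.1 / 7.4% | 7.5 / 8.3 / 9.1% |
| 25% | 4.3 / 6.5 / 9.0% | 5.0 / 6.25 / 7.7% |
| 21% | 4.0 / 6.2 / 8.9% | 4.4 / 5.7 / 7.3% |

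A mix shift common to both members of a pair largely cancels in the slope difference. The middle column is a between-arm bias only to the extent that the shift occurs in intervention communities alone.

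**Assay change.** A step in the community mean at mid-intervention (t₀ = 0.75 yr) gives a fitted end-of-trial change of [0.409 × (1.125 − 0.614)/0.237] × 1.5 = 1.32 times the step. Here 0.409 is the fraction of cases after t₀, 1.125 their mean time and 0.614 the overall mean time. If a hospital with half of a community's cases moved to an assay reading 20% differently (assumed), the 10% step would read as about 13% in that community.

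**After the change.** In ICD 410 patients, with CPK as a multiple of the local upper limit of normal, a pure change in AMI share gives 0%. A recalibration matched by its upper limit also gives 0%, and a true 10% fall reads as 10%.

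**The case against.** Several points on the other side stand.

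- A reader might infer that the expected rise in false positives dilutes the CPK average. In Section IV.G.3 (item h) and Section XI.B.5, these are patients sent home from the ED. They are not admitted and never enter the average. Only additional admissions can shift the mix.
- True positives are also expected to rise, and Section IV.F chose patients with cardiac diagnoses partly because it expects them to be more stable across communities and over time. The net direction is therefore not settled by the documents.
- A reader might say that the average mostly reflects AMI share. It does not. A 1% change in AMI CPK moves the mean by s·m/A %, and a 1% relative change in share moves it by s(m − 1)/A %, which is always less. At s = 0.50 and m = 5 these are 2.5/3 = 0.83% and 2.0/3 = 0.67%.
- A reader might infer that non-standardized assays bias the comparison. Constant differences between hospitals cancel in within-community slopes if hospital mix is stable. Section VII.A.3.b expects consistency within each institution, and drift unrelated to arm adds noise rather than bias. Nor does the protocol state why it collects upper limits of normal.
- The Section XI.B.5 measures are introduced as examples, and Section XI.A.5 already allows appropriate transformations, so a log transformation is a detail for later.
- Restricting to ICD 410 has its own weakness. The code is assigned after treatment, so a patient whose infarct was limited by early treatment might be coded elsewhere.

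None of this removes the conflict of populations: item c fixes a population that contradicts Section IV.G.3.b.

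**Conclusion.** The point holds as a conflict between the outcome definition and the analysis, with a real but bounded effect on interpretation. Followed as written, Section XI.B.5 mixes the AMI share into a measure meant to estimate infarct size, and it understates any true change. The conflict itself needs no outside figure. The sizes above rest on assumed CPK ratios, an assumed 20% rise in non-AMI cases in one arm only, and AMI shares of 21-50%. They illustrate what could appear and do not predict what will. The assay issue is a secondary matter of precision. Peak CPK is one measure of one secondary outcome, and Section VII.A.3.b also assesses severity by hemodynamic instability and ventricular arrhythmias. The correction is worth making, but the primary analysis is not affected.

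**What to change.** Reword item c of the continuous measures in Section XI.B.5 to peak CPK in patients with an ICD 410 discharge in whom it is measured, expressed as a multiple of the hospital's upper limit of normal in force at the draw. Compare it by the same two-stage slope method. This agrees with Section IV.G.3.b, and the scaling guards against assay changes over time. Keep the analysis in all primary patients as a sensitivity analysis, since ICD 410 is assigned after treatment, and state which definition of primary patients it uses.

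The cost is wording: diagnosis codes, peak values and upper limits of normal are already to be collected. The price is fewer patients per community and the selection issue just named.

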APPENDIX B: PUBLICATIONS, PRESENTATIONS AND ANCILLARY STUDIES PROCEDURES

A. Definitions

1. Main Papers and Presentations

Main papers and presentations are those reporting results dealing with the main hypotheses of the randomized controlled trial (i.e., primary and secondary end points, the design of the trial) as well as papers and presentations using the common data set. In general, main papers and presentations refer to use of data from all five sites.

2. Other Papers and Presentations

Other papers and presentations are those not encompassed by the above category; they relate to work done in ancillary studies (studies not relating to the original main hypothesis) or by a single center or a limited number of centers (using data not from all five sites).

B. Proposal and Approval Process

- 1. To initiate the process that might lead to a presentation at a scientific meeting, or writing a paper for publication, all REACT investigators and professional staff are invited to submit written proposals for abstracts or for papers to the REACT PPAS Committee.
- 2. The proposal should clearly state the research question or hypothesis and include a brief background statement to clarify the purpose and importance of the research question. If approved to go forward, a writing group will be formed, as specified below.

C. Selection of Writing Group Members and Writing Group Chairperson

- 1. As soon as the concept for an abstract or paper has been identified and approved by the PPAS Committee, the chairman of the committee will communicate with all centers requesting nominees of qualified and interested investigators to participate as members of a writing group for that paper, as well as seeking the rationale for each nominee for the writing group. The request for nominees will include a specific date (deadline) for submission of nominations.
- 2. The PPAS committee will select from the submitted list of nominees the membership of the writing group for each paper and will also identify a lead person for that writing group, so that the group may expeditiously proceed with the task. In general, the proposer of the idea for the paper or abstract will be the lead person.
- 3. It is the responsibility of the lead person to communicate with other writing group members, to develop a detailed manuscript outline, to identify data and analysis needed from the Coordinating Center, and to assume leadership in writing the manuscript. In general, the lead person will be the first author of the paper.
- 4. To expedite publication, one or more meetings of the writing group may be necessary, but in view of cost limitations, it is recommended that such meetings be kept to a minimum or, to the degree possible, be incorporated as part of other

scheduled meetings, such as REACT Steering Committee meetings or national scientific meetings.

5. The PPAS Chair and Committee are charged with the task of periodic systematic review of the work of all writing groups, aiding and encouraging members as appropriate, revising their membership or reconstituting the group membership, with written notification, when indicated. It is the intent that selection of writing committee members be equitable and fair to all groups and individuals participating in this collaborative program, including encouragement of participation by younger professional colleagues, with due regard paid to exceptional efforts of groups or individuals.

D. Preparation and Submission of Papers

The following steps should be followed in the preparation of REACT manuscripts. The lead person of each writing group should:

- 1. Contact each writing committee group and review the specific charge to the group;
- 2. Draft dummy tables which each member of the writing group would consider appropriate and needed for writing the manuscript;
- 3. Be aware that the Coordinating Center will process all requests for data and analysis according to the overall priorities of the REACT study.
- 4. Collate comments and dummy tables, solicit opinions of the writing group members, and when a consensus is reached, will submit the dummy tables (or data and analysis requests) to the Coordinating Center with copies to the Chairman of the PPAS Committee;
- 5. Obtain the input from every member of his/her group. If any member of the writing group does not respond to the lead person's request, or does not contribute to the writing of the paper, the lead person may request a replacement from the PPAS Committee. Members of each REACT writing group should participate actively in the writing, and review of the paper assigned to that group. Input from every member of the writing group should be encouraged and adhered to by all groups.
- 6. Approve the final version of the paper before its submission to the PPAS Committee. All members of the writing group should have seen the final draft before its submission to the PPAS Committee;
- 7. Perform his/her duties under the review of the PPAS Committee. If in the judgment of the PPAS Committee a writing group is not working well, and if there is an unjustifiable delay in writing the paper assigned to it, the PPAS Committee may change either the lead person or the entire membership, if in the Committee's judgment this action will expedite the writing of that particular paper.
- 8. Ensure that, in general, membership of writing groups is restricted to REACT investigators and professional staff, including the Coordinating Center and the project office at the NHLBI. Others not formally associated with REACT may become involved in some aspects of data analysis and publication if sponsored

Version 07/01/96

by a REACT principal investigator, and approved by the REACT PPAS Committee.

E. Authorship and Clearance

- 1. For main papers and presentations, names of members of the writing group shall be listed as authors in the masthead, with the addition of the phrase "for the REACT Study Group." The lead person of the writing group, with the concurrence of other members of the group, should determine the order of authorship. The lead person may choose to add REACT investigators to the authorship who are not on the writing group. A major criterion for order of authorship shall be the effort and contribution made by the members of the writing group in preparation of the manuscript. Disagreement about the order of authors which cannot be resolved by the chairman of the writing group will be resolved by the REACT PPAS Committee.
- 2. The phrase "for the REACT Study Group" added after the names of the authors in the masthead is optional in papers reporting local data, or ancillary studies using local data.
- 3. A credit roster of all major committees, units, and REACT centers with their members (generally no more than ten persons from each center) is to appear at the end of each main paper (printed as an appendix). It is the responsibility of the Coordinating Center to solicit, obtain and prepare the final list for inclusion in each REACT paper. Reprints should be ordered and supplied to the Coordinating Center.
- 4. All requests for reprints of main papers should be directed to the REACT Coordinating Center. Requests for reprints of other papers reporting data from a limited number of centers (less than the five sites) should be directed to the lead author (or the author's designee).
- 5. The REACT Steering Committee shall have the final authority to review and approve all REACT papers including papers on ancillary studies, substudies, or local center data. It is the responsibility of the chairman of the PPAS Committee to present the recommendation of the Committee to the REACT Steering Committee in a timely fashion, and to solicit the approval of that body without delay.
- 6. If an NHLBI staff member is listed as an author on a REACT article, approval of the article must be obtained by the NHLBI. To expedite the approval, it is recommended that the article be submitted simultaneously to the PPAS Committee and the NHLBI.
- 7. The chairman of the PPAS Committee will be required to submit a final draft of each REACT paper to the REACT Coordinating Center for final check on accuracy of the data. This will be done simultaneously as the paper is submitted to the REACT Steering Committee for review.
- 8. The Coordinating Center staff will be requested to submit their review within a reasonable time limit (generally not to exceed one month), and provide feedback to the chairman of the PPAS Committee as soon as possible.

- 9. Since not all circumstances that might cause disagreement among REACT investigators on the merit of a given paper can be foreseen, these disagreements should be resolved by the REACT PPAS Committee, and ultimately by the Steering Committee, if the PPAS Committee remains divided on the issue.
- 10. Every effort should be made to accommodate the expression of differing interpretations and alternate analyses within the body of each manuscript, so that all points of view are represented to the satisfaction of every participant.

F. Preparation and Submission of Abstracts for National and International Meetings

- 1. The Coordinating Center will maintain a current list of all relevant meetings and their deadlines for submission of abstracts.
- 2. All abstracts of main, other, and ancillary study papers must be approved by the PPAS Committee before they are submitted to any national or international organizations. Abstracts submitted to the Committee for review should be accompanied, if appropriate, by copies of tables and graphs to support the conclusions of the abstract. It is understood that some descriptive abstracts may not require data submission or the data may be contained in the abstract. In order for the Coordinating Center to meet the request of REACT investigators for data analysis for abstracts, and allow sufficient time for writing the abstract, the writing groups, or individuals submitting the abstract, should be selective and timely in their data requests. That is, only tables which relate to the major topics of the abstract should be requested. Detailed tabulations dealing with special topics should be reserved for the preparation of the text for meeting presentations or for the manuscript for publication. Generally, five or six tables should be sufficient. On rare occasion, examination of these five or six tables may necessitate one or two additional tables. In these situations, the Coordinating Center should meet these additional requests in a timely basis, if at all possible.
- 3. Any member of the REACT Study Group may prepare an abstract on a subject appropriate to the REACT investigation. Such an abstract may be based on the topic already assigned to a writing group, in which case the person preparing the abstract should be a member of that writing group or, the abstract may be on an entirely new topic, in which case it could originate from any investigator member of the REACT Study Group.

If an abstract is submitted for a topic for which there is no writing group, and if the topic and the abstract is approved, a writing group will be activated. Regardless of the nature of the abstract, it must be approved by:

- a. a REACT writing group if that abstract deals with the topic assigned to that group; and
- b. the REACT PPAS Committee.
- 4. In general no abstract shall be submitted to any national or international organization for consideration prior to approval of the PPAS Committee. If the REACT PPAS Committee disapproves of an abstract already submitted, the author(s) will be required to withdraw that abstract immediately. The time limit

Version 07/01/96

for review and approval of an abstract by the PPAS Committee should not exceed 2-3 weeks after the PPAS chairman has received the abstract.

- 5. If an abstract is prepared on a topic for which a writing group has not yet been selected, it is the responsibility of the PPAS Committee to select a writing group as soon as the content of the abstract is approved. The REACT Coordinating Center should have a representative on this writing group, as in most REACT writing groups, to expedite communication with the Coordinating Center and facilitate timely analysis of data and preparation of art work and slides for presentation.
- 6. The selection of the person who will present the material in the abstract at the respective national or international meeting will be at the discretion of the respective writing group (if any). If a writing group has not been constituted, the PPAS Committee will make the selection of the presenter. In general, this will be the person proposing the abstract. Regardless of who selects the presenter, the selection must be approved by the PPAS Committee.

G. Dissemination of Information

1. Prior to abstract presentation, the responsible writing group is required to submit a copy of visual aids, including tables and graphs, of the paper to be presented, to the PPAS Committee for review, prior to the date of the particular meeting. Unless these tables and graphs are approved by the PPAS Committee, that paper shall not be presented, even though its abstract may have been approved for presentation. Also, it is desirable to submit to the PPAS Committee a copy of the text for presentation, if available. Each presentation shall have a sentence at the beginning identifying it as the work of the REACT Study GROUP, and that it is presented by that particular member "for the REACT Study Group". Likewise, the presenters of REACT ancillary studies or local center data, are encouraged to share their visual aids and text of their presentations with the PPAS Committee. These presentations need not include the phrase "for the REACT Study Group."

- 2. Once a main paper has been presented at a scientific meeting, the tables used should be available to REACT investigators and may be used by them at other scientific meetings. However, such subsequent presentations should not appear in published form unless the data in the original paper are already published.
- 3. In the case of papers scheduled for presentation before an organization issuing press releases, the presenter may submit, for release to the press, the text of the presentation after it has been approved by the PPAS Committee . If the presentation is based on a manuscript not yet accepted for publication in a peer review journal, a sentence must be included on the front page indicating the preliminary nature of the results.
- 4. Slides for use at national or international meetings or for publications will be sent to REACT Principal Investigators by the Coordinating Center.
- 5. A standard set of slides, representing the major results of REACT will be produced by the Coordinating Center for each study center.

H. Invitations to REACT Investigators for Presentation of REACT Materials

The REACT Study Group welcomes opportunities to participate and present reports at national and international scientific meetings. When an invitation is received by a member of the REACT Study Group, REACT policies with regard to publications and presentations must be followed.

- 1. When a personal invitation is received by a REACT investigator to make a presentation, this invitation shall be sent to the PPAS Committee for review and approval.
- 2. When an invitation is extended to more than one investigator, or if it comes to the chairperson of the Steering Committee or the chairperson of the PPAS Committee, requesting a representative of the REACT study, the PPAS Committee shall decide who is to represent REACT.
- 3. All presentations in response to such invitations are to be based on published REACT reports unless approved beforehand by the PPAS Committee.
- 4. Any presentation of unpublished REACT data must be reviewed and approved by the PPAS Committee prior to the date of presentation.
- 5. Requests received by Principal Investigators or their staff, to present or discuss at local meetings (city, state or regional) any previously published REACT data, need no prior clearance by the PPAS Committee. All local presentations must be reviewed and approved by the principal investigator for the center making the presentation. REACT Investigators should be encouraged to accept such invitations. It is requested that principal investigators receiving such requests notify the Coordinating Center so the Center can keep record of these presentations.
I. Use of REACT Material for Graduate Student Theses or Dissertations

- 1. All requests for use of REACT data by students will be reviewed by the PPAS Committee.
- 2. The student requesting REACT data must be associated with an investigator in the REACT study. The REACT investigator shall act as the student's "sponsor" with regard to the data request.
- 3. REACT data may not be used by students if the data related to the REACT main paper are in progress or if the PPAS Committee deem the data necessary for a future paper.
- 4. If the PPAS Committee recommends approval for the use of the requested data, a review group will be established and will include the student as convener of the group.
- 5. The review group will take no action regarding the paper until the student has completed and defended the thesis or dissertation, provided this occurs in a reasonable length of time. (The student's sponsor will be requested to report on the student's progress to the PPAS Committee).
- 6. The students must include in the completed thesis the following:
 - a. a statement acknowledging REACT study for use of the data;
 - b. a statement indicating that opinions, ideas, and interpretations included in the thesis or dissertations are those of the student alone and not necessarily those of the REACT Investigators.
- 7. When the thesis or dissertation has been completed as determined by the sponsor, the dissertation review group will proceed to prepare the paper(s) for publication. A writing group will be formally constituted and will be composed primarily of review group members. The student should be given the opportunity to take the lead on the paper.
- 8. The standard REACT publication policy will apply to any material published from the thesis or dissertation.
- 9. The REACT Study Group reserves the right to proceed with preparing a paper for publication on the thesis or dissertation topic if, in the view of the PPAS Committee, the student has not made reasonable progress on completing the thesis or dissertation.

J. Other Papers and Presentation, and Other Matters

- 1. Members of REACT centers who identify additional papers that draw on data collected by all REACT centers should communicate in writing the general topic or title of the paper they wish to have considered for publication to the chairperson of the PPAS Committee. The proposal should state the rationale, background, hypothesis or purpose, and methods. Upon receipt, the policy and procedures described above shall apply.
